7.2.1.3. Dose-Limiting Toxicity Determination (Part A)

Dose-limiting toxicity is defined as an AE during Cycle 1 (first 21 days from Day 1 in Cycle 1) that is possibly related to the study drug(s) (olaratumab and/or doxorubicin) and fulfills any one of the following criteria using the National Cancer Institute (NCI) Common Terminology Criteria for Adverse Events (CTCAE) (v4.03):

- CTCAE Grade 3 or above nonhematologic toxicity. Exceptions will be made for:
 - Nausea, vomiting, diarrhea, constipation, or electrolyte abnormality that can be controlled with treatment.
 - Fatigue and anorexia.
 - Transient (ie, ≤ 1 week) Grade 3 elevations of ALT and/or AST without evidence of other hepatic injury.
- Febrile neutropenia.
- Grade 4 anemia.
- Grade 4 neutropenia lasting >1 week.
- Grade 4 thrombocytopenia, or Grade 3 thrombocytopenia requiring platelet transfusion.
- Toxicities which require dose reduction or omission of study drug(s) (olaratumab and/or doxorubicin) during Cycle 1.
- Any other significant toxicity deemed by the primary investigator and Lilly CRP/clinical research scientist (CRS) to be dose limiting (eg, any toxicity that is possibly related to the study medication that requires the discontinuation of the patient from the study during Cycle 1).

In the event of a Grade 3 or 4 infusion-related reaction, the patient will be replaced; however, the event will not be considered a DLT. An evaluable patient for DLT is defined as a patient who takes 100% of planned dose in Cycle 1 or a patient who experiences DLT in Cycle 1. If a patient is judged to be non-evaluable for DLT, the patient will be replaced by a new patient.

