7.2.2. Dose Adjustments and Delays

7.2.2.1. Delays and Omission

In the case that olaratumab or doxorubicin cannot be administered due to any reason including toxicity, the administration can be delayed beyond the time window within the cycle. If the planned administration cannot be conducted within the cycle, the dose is defined as an omission. For olaratumab-related toxicity \geq Grade 3 not adequately controlled with appropriate supportive care, olaratumab should not be administered until the toxicity becomes \leq Grade 2 or returns to pretreatment baseline.

Part A

Illustrative examples of dose adjustments are shown in [Attachment 5](#).

In general, discontinuation of 1 study drug (olaratumab or doxorubicin) will not necessitate discontinuation of the other study drug. Dose omission, delays, or discontinuation of olaratumab due to an olaratumab-related toxicity will not alter those of doxorubicin. Similarly, olaratumab therapy should not be altered for doxorubicin-related toxicity.

Day 1 of Cycles 2 through 7 (the first cycle of olaratumab monotherapy for the patients who receive doxorubicin on Cycle 7 or later, by reason that cumulative dose of doxorubicin does not reach 500 mg/m² during the first 6 cycles) is defined as the 21st day after the first doxorubicin administration in the previous cycle. Day 1 of Cycle 8 (the second cycle of olaratumab monotherapy for the patients who receive doxorubicin on Cycle 7 or later, by reason that cumulative dose of doxorubicin does not reach 500 mg/m² during the first 6 cycles) or any of the following cycles is defined as the 21st day after the first olaratumab administration in the previous cycle. In the case that olaratumab is delayed or omitted for any reason (including AEs), administration of doxorubicin will continue according to the original schedule. Dose delay of olaratumab on Day 8 is allowed until 7 days before Day 1 of the following cycle. Upon

resolution of the event(s) causing the delay and omission in olaratumab administration, olaratumab treatment will resume according to a Day 1/Day 8 schedule. In this study, every effort will be made to synchronize administration of olaratumab and doxorubicin according to the original dosing schedule; therefore, olaratumab may be administered for up to 4 weeks in a row.

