7.2.2.3. Guidelines for Olaratumab Dose Reduction

7.2.2.3.1. *Hematologic Toxicity*

For Grade ≤ 2 hematologic toxicity, no dose modification is required. For Grade 3 toxicity not adequately controlled with appropriate supportive care (including hematopoietic growth factors, if indicated), olaratumab should not be administered until toxicity \leq Grade 2, or has returned to pretreatment baseline; at this time, dose should be reduced to 12 mg/kg and treatment resumed. In the case of Grade 4 hematologic toxicity associated with olaratumab, olaratumab should not be administered until toxicity is \leq Grade 2, then dose should be reduced to 10 mg/kg and treatment should resume.

7.2.2.3.2. *Nonhematologic Toxicity*

Specific guidelines for dose reduction in patients who experience infusion-related reactions while receiving treatment with olaratumab are found in Section 8.1.3.4.

General guidelines for dose modification for other nonhematologic toxicities related to olaratumab are shown in Table JGDK.7.2.

Table JGDK.7.2. General Guidelines for Dose Modification Due to Nonhematologic Toxicities Related to Olaratumab

Reaction Grade	Required Dose Modification
Grade 1	No dose modification is required.
Grade 2	At the investigator's discretion, the patient may continue to receive olaratumab per protocol, provided that the event does not pose a serious health risk or is easily treated. If necessary, the patient may be dose reduced up to 2 dose reductions (to 12 mg/kg and subsequently to 10 mg/kg) during the study.
Grade 3	For a Grade 3 toxicity not adequately controlled with appropriate supportive care, the dosing must not be administered until toxicity is \leq Grade 1 or has returned to pretreatment baseline; treatment may then resume at a reduced dose of 12 mg/kg (15 mg/kg if the toxicity occurs during Cycle 1 of Cohort 3 in Part A). If toxicity recurs after therapy resumes, a second dose reduction (to 10 mg/kg) is permitted. If more than 2 toxicity-related olaratumab dose reductions are required, treatment with this agent will be permanently discontinued.
Grade 4	The dose must not be administered until dose toxicity is \leq Grade 1 or has returned to baseline. Treatment may then resume with the dose reduced to 10 mg/kg (15 mg/kg if the toxicity occurs during Cycle 1 of Cohort 3 in Part A). If toxicity recurs after therapy resumes, olaratumab treatment will be discontinued.

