8.1.1. Safety Data Collection and Review

Investigators are responsible for monitoring the safety of patients who have entered into this study and for alerting Lilly or its designee to any event that seems unusual, even if this event may be considered an unanticipated benefit to the patient.

The investigator is responsible for the appropriate medical care of the patient during the study.

The investigator remains responsible for following, through an appropriate health care option, AEs that are serious, considered related to study treatment or the study, or that caused the patient to discontinue before completing the study. The patient should be followed until the event is resolved, the event is no longer considered to be drug-related, the event becomes stable or returns to baseline, a new treatment is initiated for the patient, or the patient dies or is lost to follow-up. Frequency of AE and SAE follow-up evaluation is left to the discretion of the investigator.

The timing of all safety evaluations is shown in the Study Schedule ([Attachment 1](#)). [Table JGDK.8.1](#) presents a summary of AE and SAE reporting guidelines. [Table JGDK.8.1](#) also shows which database or system is used to store AE and SAE data.

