Attachment 1. Protocol I5B-JE-JGDK Study Schedule

Study Schedule for Protocol I5B-JE-JGDK – Part A: Screening and Cycle 1

Relative day within a cycle	Screening			Cycle 1				Comments
	≤21	≤14	≤7	1	2	3	8	
Informed consent	X							Informed consent form signed (prior to performance of any protocol-specific tests/procedures and patients must be ≥ 20 years of age).
Medical history		X						Includes past and current medical conditions, treatments, and alcohol/tobacco use.
Pregnancy test			X					Serum or urine: Pregnancy test is only required for females of child-bearing potential.
Physical examination		X		X ^a			X ^a	Includes medical interview, height (at screening only), weight, and body surface area.
Vital signs		X		X ^b			X ^c	Pulse rate, respiration rate, temperature, and supine blood pressure will be measured.
ECOG performance status		X		X ^a				
NYHA classification		X						
ECG	X			See Attachment 4				Screening ECGs will be performed locally. Obtain ECGs before any associated blood draws.
Echocardiogram	X							Echocardiogram will be performed locally. Data obtained before patient's consent may be used as the screening data if the relevant tests are conducted within the allowed time window.
Hematology		X		X ^a			X ^a	
Serum chemistry		X		X ^a			X ^a	
Coagulation		X		X ^a				
Urinalysis		X		X ^a				
Hepatitis B and C virus	X							Includes tests for Hepatitis B surface antigen, Hepatitis B surface antibody, Hepatitis B core antibody and Hepatitis C antibody. Test for Hepatitis B DNA will be performed as necessary.
CTCAE v4.03 grading	X			X	X ^d	X ^d	X	Throughout study as needed.
Concomitant medications	X			X	X ^d	X ^d	X	
Radiological tumor assessment	X							Data obtained before patient's consent can be used as screening data if the relevant tests are conducted within the allowed time window.
PK sampling				See Attachment 4				
Immunogenicity sampling				See Attachment 4				
Blood sampling for translational research				X ^a				Plasma samples will be collected from whole blood.
Tumor tissue submission				X				If available.
Olaratumab administration				X ^e			X ^e	
Doxorubicin administration				X	X ^d	X ^d		

Study Schedule for Protocol I5B-JE-JGDK – Part A: Screening and Cycle 1

Abbreviations: CTCAE = Common Terminology Criteria for Adverse Events; DNA = deoxyribonucleic acid; ECG = electrocardiogram; ECOG = Eastern Cooperative Oncology Group; NYHA = New York Heart Association; PK = pharmacokinetic.

- a Predose only.

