- b Vital sign measurements will be obtained prior to and at the completion of each olaratumab administration, and prior to each doxorubicin administration.
- c Vital sign measurements will be obtained prior to and at the completion of olaratumab administration, and approximately one hour following the completion of olaratumab administration.
- d Cohort 1 only.
- e 15 mg/kg in Cohort 1 and 2, and 20 mg/kg as loading dose in Cohort 3.

Study Schedule for Protocol I5B-JE-JGDK – Part A: Cycle 2 and beyond

Relative day within a cycle	Cycle 2-6				Cycle 7-n		Follow-Up ^c	Comments
	1a	2	3	8	1b	8		
Allowance (days)	+3			±3d	+3	±3	±5	
Informed consent	X							Informed consent form signed (prior to beginning of Cycle 2).
Pregnancy test	X ^e				X ^e		X	Should be performed approximately every 6 weeks (i.e., at the beginning of Cycle 3 and every other cycle thereafter) during the study.
Physical examination	X ^e				X ^e		X	Includes medical interview, weight, and body surface area.
Vital signs	X ^f			X ^f	X ^f	X ^f	X	Pulse rate, respiration rate, temperature, and supine blood pressure will be measured.
ECOG performance status	X ^e				X ^e		X	
ECG	See Attachment 4							Obtain ECGs before any associated blood draws.
Echocardiogram	X ^e				X ^e		X	Should be performed locally at Cycles 5 and 7 (within 3 days prior to the treatment on Day 1, but re-measurement is not necessary in case of dose delay of Day 1) and follow-up visit.
Hematology	X ^e			X ^e	X ^e	X ^e	X	
Serum chemistry	X ^e			X ^e	X ^e	X ^e	X	
Coagulation	X ^e				X ^{e,h}		X	
Urinalysis	X ^e				X ^{e,h}		X	Should be performed approximately every 6 weeks (ie, at the beginning of Cycle 3 and every other cycle thereafter).
CTCAE v4.03 grading	X	X ^g	X ^g	X	X	X	X	Throughout study as needed.
Concomitant medications	X	X ^g	X ^g	X	X	X	X	
Radiological tumor assessment	X				X		X	Prior to Cycles 3 and 5 (no more than 14 days prior to Day 1 Cycle 3 and 5), then every 2-4 cycles as clinically indicated.
PK sampling	See Attachment 4							
Immunogenicity plasma sampling	See Attachment 4							
Olaratumab administration	X			X	X	X		
Doxorubicin administration	X	X ^g	X ^g					

Study Schedule for Protocol I5B-JE-JGDK – Part A: Cycle 2 and beyond

Abbreviations: CTCAE = Common Terminology Criteria for Adverse Events; ECG = electrocardiogram; ECOG = Eastern Cooperative Oncology Group; PK = pharmacokinetic.

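### Part A counts laboratory DLTs over 21 days, but the only scheduled post-dose safety sample in that window is taken before the Day 8 dose, so silent later events can be missed and durations are not measured by schedule

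*Protocol*

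**What the plan says.** **DLT definition (Protocol 7.2.1.3).** The window is the first 21 days of Cycle 1. Grade 4 anemia and Grade 4 thrombocytopenia count whatever their duration. Two criteria depend on duration. One is "Grade 4 neutropenia lasting >1 week". The other is the exemption for transient Grade 3 "elevations of ALT and/or AST without evidence of other hepatic injury", where transient means one week or less.

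**Laboratory schedule (Attachment 1, Part A, Screening and Cycle 1).** The Cycle 1 columns are Days 1, 2, 3 and 8. Hematology and serum chemistry are marked on Days 1 and 8 only, both with the footnote "a Predose only". The next scheduled sample is before dosing on Day 1 of Cycle 2, which Section 7.2.2.1 says "is defined as the 21st day after the first doxorubicin administration in the previous cycle". That is Day 22, and Attachment 1 allows 3 more days.

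**Decision rule (7.2.1.5).** With 6 evaluable patients, 0 or 1 DLT means tolerable, 2 lead to review, and 3 or more mean not tolerable.

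**Analysis (SAP 6.11.2).** DLTs are tabulated by cohort and listed. Neither this section nor Protocol 7.2.1.3 says how a duration is to be judged from dated counts.

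**The concern.** A criterion counted over 21 days, and in two cases by how long an abnormality lasts, needs measurements over those days. After the Day 8 predose sample the plan requires none until the window has closed. A Grade 4 cytopenia or transaminase rise without symptoms can start and resolve between Day 9 and Cycle 2 without meeting a scheduled test. An abnormality seen on Day 8 has no scheduled follow-up from which to judge whether it passed one week.

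One patient separates 1 of 6 from 2 of 6, and this is the Part A tolerability decision. Cohort 2's result opens Cohort 3 (7.2.1.4) and informs the decision to join the global Phase 3 program (SAP 6.15). Cohort 3 was added to confirm tolerability of the 20 mg/kg loading dose (5.2.1). That dose is given on Days 1 and 8 of Cycle 1, yet the second one has no scheduled safety laboratory test before Day 22.

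Neutropenia is a relevant toxicity here. Section 5.1 reports a slight increase with this combination in the earlier randomized study, and Section 7.5 does not permit primary prophylaxis with G-CSF.

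**Working it through.** **The plan's own rule.** 1/6 = 16.7%, below the 33% limit in 7.2.1.5; 2/6 = 33.3%, not below it. The rule is consistent with its stated threshold. Section 10.1 says the 6 per cohort rests on no power calculation.

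**Inputs.** Window Days 1–21 (7.2.1.3). Post-dose sample inside the window: Day 8 predose (Attachment 1). Next sample: Day 1 + 21 = Day 22 (7.2.2.1, and the dosing scenarios in Attachment 5), or 22 + 3 = Day 25 with the allowance.

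**Uncovered days.** 21 − 8 = 13 of 21 days (62%), namely Days 9–21.

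**Onset-day counts.** Take an episode of *L* consecutive days starting on Day *s*, with *s* at least 2. It is seen on sampling Day *t* only if *s* ≤ *t* ≤ *s* + *L* − 1. The shortest whole-day episode longer than a week has *L* = 8.

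- *Must end by Day 21:* onsets 2–14, so 13. Onsets 2–8 (7) include Day 8. Onsets 9–14 (6) do not.
- *May run past Day 21, Cycle 2 on Day 22:* onsets 2–21, so 20. Onsets 2–8 meet Day 8 and onsets 15–21 meet Day 22. Onsets 9–14 (6) meet neither.
- *The same, Cycle 2 on Day 25:* only onsets 18–21 meet Day 25. Onsets 9–17 (9) meet neither.

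Onset days that meet no scheduled count:

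| Episode length | Ends by Day 21 | May run on, counts Days 8 and 22 | May run on, counts Days 8 and 25 |
|---|---|---|---|
| 5 days | 11 of 16 | 11 of 20 | 14 of 20 |
| 8 days | 6 of 13 | 6 of 20 | 9 of 20 |
| 13 days | 1 of 8 | 1 of 20 | 4 of 20 |
| 8 days, Day 15 count added | 0 of 13 | 0 of 20 | 2 of 20 |

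The 5-day row matters only for criteria without a duration, such as Grade 4 thrombocytopenia. A 5-day Grade 4 neutropenia is not a DLT under the duration criterion, and a 5-day Grade 3 ALT/AST rise without other hepatic injury is exempt.

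**Can duration be established?** To include both Day 8 and Day 22 an episode must last at least 22 − 8 + 1 = 15 days, so no 8-day episode meets two scheduled counts. Suppose a value is normal on Day 1, abnormal on Day 8 and normal on Day 22. The episode could have lasted 1 day (Day 8 alone) or 21 − 2 + 1 = 20 days (Days 2–21), which falls on both sides of the one-week line. Even with a Day 15 count, only 2 of 20 eight-day onsets (Days 8 and 15) meet two counts, or 1 of 20 if Cycle 2 starts on Day 25. A written duration rule is needed in any case.

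**Sensitivity of the decision.** The share of DLTs missed is not in the documents, so the shares below are assumptions. With true rate *p* and missed share *m*, let *q* = *p*(1 − *m*). Then P(0 or 1 of 6) = (1 − *q*)^6 + 6*q*(1 − *q*)^5. At an assumed *p* = 0.33:

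| Share missed | P(called tolerable) |
|---|---|
| 0% | 0.358 |
| 10% | 0.427 |
| 25% | 0.540 |
| 50% | 0.741 |

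**The case against.** **Attachment 1 is a minimum schedule.** Unscheduled tests are allowed. Section 8.1.1 requires related adverse events to be followed, and Section 8.4 lets the sponsor modify collection times. The last criterion in 7.2.1.3 lets the investigator and sponsor call any other significant toxicity dose limiting. Table JGDK.7.3 uses the same neutropenia duration for doxorubicin dosing, so investigators have a reason to measure it. Cohorts 2 and 3 also attend after Day 8 for PK and ECG. All of this is true, but none of it requires a count on Days 9–21. Section 8.1.1 adds that "Frequency of AE and SAE follow-up evaluation is left to the discretion of the investigator"; Section 8.1.2 ties routine assessment to the same schedule; and the hepatic trigger in 8.1.4 needs ALT and bilirubin raised together.

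**Many DLTs are caught another way.** This stands. Symptomatic events such as febrile neutropenia prompt their own tests. Toxicity that leads to reduction or omission of a Cycle 1 dose is itself a DLT, and Section 7.2.2.3.1 feeds that route: "In the case of Grade 4 hematologic toxicity associated with olaratumab, olaratumab should not be administered until toxicity is" Grade 2 or lower. But the last Cycle 1 dose is due on Day 8. Section 7.2.2.1 says "Dose delay of olaratumab on Day 8 is allowed until 7 days before Day 1 of the following cycle", that is, by Day 15, so this route closes before the window does.

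**It may be too late.** Amendment (b), dated September 2018, says enough data had been obtained for the primary objective (5.2.2). More Part A Cycle 1 patients are therefore unlikely, and a changed schedule cannot help those already treated. Counting undetermined durations both ways helps only for events that were seen; unsampled events can only be flagged. Both points stand and limit the remedy.

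**The counts are not an effect size.** Also true. They weight onset days equally for counting only, and the documents give no onset distribution.

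**Conclusion.** The concern holds and should be fixed. The Cycle 1 laboratory schedule cannot by itself measure the criteria that 7.2.1.3 applies. Thirteen of 21 window days have no scheduled test, the second olaratumab dose has none after it inside the window, and no qualifying 8-day episode meets two scheduled counts. Silent events starting after Day 8 may be under-counted. For ALT/AST, an undetermined duration can be misclassified in either direction.

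Confidence in the schedule gap is high. Its effect on the tolerability decision cannot be sized from the documents: the probabilities above depend on assumed missed shares and an assumed true DLT rate. Clinically evident DLTs are largely unaffected. The reading assumes that the extracted Cycle 1 table has lost no column. Its headings agree with its footnotes, and the Part B table likewise ends at Day 8.

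**What to change.** 1. **Any further Part A enrolment.** Reconcile Protocol 7.2.1.3 with Attachment 1 so that the timing of Cycle 1 laboratory tests can measure the DLT criteria. One example is the visit 168 h after the Day 8 dose, which Cohorts 2 and 3 already attend for PK and ECG (Attachment 4). Cost: one extra routine tube per patient. Cohort 1 might need one short added visit; its Attachment 4 table is too broken in the extracted text to tell.
2. **Duration rule.** State in 7.2.1.3 and SAP 6.11.2 how duration is judged from dated counts, including when counts are sparse. Cost: two sentences. If the DLT calls have already been made, say that the rule was written afterwards.
3. **Patients already treated.** From the laboratory listing planned in SAP 6.11.5, show the dated Cycle 1 values behind each laboratory-based DLT call. Flag every patient with no count on Days 9–21. Report each cohort's DLT count twice, with undetermined durations counted as DLTs and as non-DLTs. Cost: a cross-reference, a flag and one tally. This step remains useful if enrolment is complete.

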7.2.1.4. Initiation of Cohort 2 and 3 in Part A

After first 3 patients from Cohort 1 are enrolled, Cohort 2 can be opened based on safety assessment and after discussion between the investigator and the sponsor. In addition, the

sponsor should consult with Safety Assessment Committee (SAC) about the appropriateness for the timing. Cohort 3 can be opened after confirmation of tolerability in Cohort 2.

7.2.1.5. Tolerability Confirmation (Part A)

Tolerability confirmation will be judged if frequency of DLT is confirmed less than 33% each of cohort. At least 6 patients will be enrolled in each cohort and evaluated for DLT during Cycle 1 (first 21 days from Day 1 in Cycle 1).

- If 0 or 1 out of 6 evaluable patients experience DLTs, it will be judged that the dose is tolerable for Japanese patients.
- If 2 patients experience DLTs at any given dose, the sponsor will examine the safety data and consult with the SAC as needed. The sponsor and the investigators will decide if the dose is intolerable or if additional patients will be enrolled to the same dose level for further investigation.
- If ≥ 3 patients experience DLTs at any given dose, it will be judged that the dose is not tolerable for Japanese patients.

7.2.2. Dose Adjustments and Delays

7.2.2.1. Delays and Omission

In the case that olaratumab or doxorubicin cannot be administered due to any reason including toxicity, the administration can be delayed beyond the time window within the cycle. If the planned administration cannot be conducted within the cycle, the dose is defined as an omission. For olaratumab-related toxicity \geq Grade 3 not adequately controlled with appropriate supportive care, olaratumab should not be administered until the toxicity becomes \leq Grade 2 or returns to pretreatment baseline.

Part A

Illustrative examples of dose adjustments are shown in [Attachment 5](#).

In general, discontinuation of 1 study drug (olaratumab or doxorubicin) will not necessitate discontinuation of the other study drug. Dose omission, delays, or discontinuation of olaratumab due to an olaratumab-related toxicity will not alter those of doxorubicin. Similarly, olaratumab therapy should not be altered for doxorubicin-related toxicity.

Day 1 of Cycles 2 through 7 (the first cycle of olaratumab monotherapy for the patients who receive doxorubicin on Cycle 7 or later, by reason that cumulative dose of doxorubicin does not reach 500 mg/m² during the first 6 cycles) is defined as the 21st day after the first doxorubicin administration in the previous cycle. Day 1 of Cycle 8 (the second cycle of olaratumab monotherapy for the patients who receive doxorubicin on Cycle 7 or later, by reason that cumulative dose of doxorubicin does not reach 500 mg/m² during the first 6 cycles) or any of the following cycles is defined as the 21st day after the first olaratumab administration in the previous cycle. In the case that olaratumab is delayed or omitted for any reason (including AEs), administration of doxorubicin will continue according to the original schedule. Dose delay of olaratumab on Day 8 is allowed until 7 days before Day 1 of the following cycle. Upon

resolution of the event(s) causing the delay and omission in olaratumab administration, olaratumab treatment will resume according to a Day 1/Day 8 schedule. In this study, every effort will be made to synchronize administration of olaratumab and doxorubicin according to the original dosing schedule; therefore, olaratumab may be administered for up to 4 weeks in a row.

If olaratumab is not administered for more than 21 days from Day 1 of the following scheduled cycle due to an olaratumab related-toxicity that does not resolve, or if more than 2 toxicity-related olaratumab dose reductions are required, treatment with olaratumab will be permanently discontinued.

In the case that doxorubicin is delayed or omitted for any reason (including AEs), administration of olaratumab will continue according to the original schedule. If doxorubicin is not administered for more than 21 days from Day 1 of the following scheduled cycle due to a doxorubicin-related toxicity that does not resolve, treatment with doxorubicin will be permanently discontinued.

If both doxorubicin and olaratumab are discontinued, the patient will be discontinued from the study.

Part B

Day 1 of each cycle (Cycle 2 and beyond) is defined as the 21st day after the first olaratumab administration in the previous cycle.

When olaratumab is not administered on the scheduled day, study therapy will resume provided resolution of the event(s) causing the delay. Dose delay of olaratumab on Day 8 is allowed until 7 days before Day 1 of the following cycle. If olaratumab is discontinued, the patient will be discontinued from the study.

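### For olaratumab-related nonhematologic toxicity of Grade 3 or above, protocol 7.2.2.1 lifts the dosing hold at Grade 2 while Table JGDK.7.2 bars dosing until Grade 1

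*Protocol*

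**What the plan says.** **Protocol 7.2.2.1 (Delays and Omission).** The hold sentence covers olaratumab-related toxicity of Grade 3 or above that is "not adequately controlled with appropriate supportive care, olaratumab should not be administered until the toxicity becomes" at or below "Grade 2 or returns to pretreatment baseline". It stands before the Part A and Part B subheadings, so it applies to both parts, and it draws no line between hematologic and nonhematologic events.

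**Protocol 7.2.2.3.1 (hematologic toxicity).** For uncontrolled Grade 3, the hold runs until toxicity is at or below "Grade 2, or has returned to pretreatment baseline; at this time, dose should be reduced to 12 mg/kg and treatment resumed". For Grade 4: "In the case of Grade 4 hematologic toxicity associated with olaratumab, olaratumab should not be administered until toxicity is" at or below "Grade 2, then dose should be reduced to 10 mg/kg and treatment should resume".

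**Protocol 7.2.2.3.2 and Table JGDK.7.2 (nonhematologic toxicity other than infusion-related reactions).** The Grade 3 row reads: "For a Grade 3 toxicity not adequately controlled with appropriate supportive care, the dosing must not be administered until toxicity is" Grade 1 or lower, or back at the pretreatment baseline. Treatment then resumes at 12 mg/kg (15 mg/kg if the event arises in Cycle 1 of Cohort 3). The Grade 4 row also requires Grade 1 or lower, or baseline. It applies whether or not supportive care controls the event, and dosing resumes at 10 mg/kg (again 15 mg/kg for Cycle 1 of Cohort 3).

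**Protocol 8.1.3.4.** A Grade 3 or 4 infusion-related reaction ends olaratumab permanently, so no restart threshold applies to it.

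**The concern.** Both texts address the same decision: when olaratumab may be given again after a severe drug-related event. For nonhematologic events they set different bars, and 7.2.2.1 sets the looser one. Its heading is where a site would look for a rule on withholding a dose. The stricter rule sits under a heading about dose reduction.

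Two things are at stake.

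- **Patient safety.** A site that follows 7.2.2.1 as written could redose a patient whom the table forbids it to dose.
- **Continuation of treatment.** Under its Part A heading, 7.2.2.1 stops olaratumab permanently if an unresolved olaratumab-related toxicity keeps it from being given for more than 21 days from Day 1 of the next scheduled cycle. An event that settles at Grade 2 can be redosed under one rule. Under the other it can keep the drug off until that limit passes.

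**Working it through.** No arithmetic applies. The check is to set the rules side by side and find the states in which they give different answers.

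**Step 1. Restart level by toxicity class and starting grade.**

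| Olaratumab-related event | 7.2.2.1 | Class-specific rule | Restart grade |
|---|---|---|---|
| Hematologic Grade 3, uncontrolled | ≤ 2 or baseline | ≤ 2 or baseline (7.2.2.3.1) | Same |
| Hematologic Grade 4 | ≤ 2 or baseline, if uncontrolled | ≤ 2 (7.2.2.3.1) | Same |
| Nonhematologic Grade 3, uncontrolled | ≤ 2 or baseline | ≤ 1 or baseline (Table JGDK.7.2) | **Differs** |
| Nonhematologic Grade 4 | ≤ 2 or baseline, if uncontrolled | ≤ 1 or baseline (Table JGDK.7.2) | **Differs** |

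The Grade 3 row of the table uses the same supportive-care condition as 7.2.2.1. In that row the difference cannot be explained by a different trigger.

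**Step 2. Where the two nonhematologic rules disagree.** Take an uncontrolled nonhematologic event of Grade 3 or 4, other than an infusion-related reaction.

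- Now at Grade 1 or lower: both rules release the hold.
- Now at Grade 2, with baseline Grade 2: both release it, through the baseline alternative.
- Now at Grade 2, with baseline below Grade 2: 7.2.2.1 releases it and the table bars dosing.
- Still at Grade 3 or above, with a lower baseline: both hold.

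The conflict is confined to the third state.

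**Step 3. Is there a rule of precedence?** None was found. The hold sentence in 7.2.2.1 does not refer to 7.2.2.3. Section 7.2.2.2 does, but only for reducing the dose. The SAP lists delays, omissions and reductions (6.11.1) and sets no dosing rule.

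**Step 4. Secondary point, Grade 4.** The 7.2.2.1 hold applies only when supportive care fails. Both Grade 4 rules in 7.2.2.3 hold the drug without that condition. Section 7.2.2.1 is therefore silent on a Grade 4 event that supportive care controls; it does not authorise dosing in that case.

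**Step 5. How many patients.** The documents give no rate for the joint event: olaratumab-related, nonhematologic, not a Grade 3 or 4 infusion-related reaction, Grade 3 or above, improved to exactly Grade 2, with a lower baseline. Protocol 5.1 reports few Grade 3 events and none of Grade 4 or 5 in the first Phase 1 monotherapy study. This suggests a small number, although monotherapy is only indirect evidence for the combination in Part A.

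**The case against.** **The table is the natural controlling rule.** It is specific to class and grade, it says must not where 7.2.2.1 says should not, and its column heading calls the modifications required. Both texts are minimum bars, so waiting for Grade 1 satisfies both. Elsewhere 7.2.2.1 ties resumption to resolution of the event, so reaching Grade 2 is not plainly a permission to redose. A careful site would probably do the right thing, and this keeps the point minor. It does not remove the conflict. The protocol never says that the table prevails, the table's own title calls its contents general guidelines, and the general sentence gives a definite end to the hold that the table contradicts.

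**A stronger reading: the conflict changes DLT classification.** A reader might reason as follows. By 7.2.2.1, "Dose delay of olaratumab on Day 8 is allowed until 7 days before Day 1 of the following cycle"; with the next Day 1 on Day 22, the limit is 22 − 7 = Day 15. A nonhematologic event still at Grade 2 on Day 15 of Cycle 1 would be dosed late under 7.2.2.1 but not dosed under the table. Then "If the planned administration cannot be conducted within the cycle, the dose is defined as an omission", and an omission required by toxicity in Cycle 1 is a DLT. The documents do not support this when read together. After uncontrolled Grade 3 toxicity the table resumes only at a reduced dose, and 7.2.1.3 also counts a toxicity requiring reduction in Cycle 1 as a DLT. The patient is a DLT under either threshold. In addition, the rationale for Amendment (b) says that enough data for the primary objective had already been obtained.

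**A stronger reading: 7.2.2.1 is at odds with 7.2.2.3 throughout.** A reader might count the Grade 4 supportive-care condition and the missing baseline alternative for hematologic Grade 4 as further contradictions. The first is silence, as shown in the working. The second matters only if the baseline is worse than Grade 2. The entry floors for neutrophils, platelets and hemoglobin make that nearly impossible, although lymphocytes have no floor.

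**A stronger reading: about six months of dosing under the faulty text.** A reader might count from approval on 28 September 2018 to March 2019. March 2019 is the estimated last visit, which follows the 28-day follow-up period. Attachment 9 also lists no change to 7.2.2, so the sentence appears to be older than this version. The documents do not give the length of exposure to the rule.

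**Conclusion.** The point holds: the hold sentence in 7.2.2.1 is wrong as written for nonhematologic toxicity. The restart level differs by one CTCAE grade (at most 2 against at most 1) for nonhematologic Grade 3 and Grade 4 events. The rules collide only when such an event has improved to Grade 2 and the baseline is below Grade 2. The hematologic Grade 3 rule agrees with 7.2.2.1, and Grade 3 or 4 infusion-related reactions are outside the point.

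Severity is minor. The practical consequences are possible redosing of a patient whom the table bars and, in Part A, a possible difference in whether the 21-day discontinuation limit is reached. The number of patients is probably small and cannot be computed. No effect on DLT classification is claimed.

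The conclusion assumes that 7.2.2.1 means what it says in covering all olaratumab-related toxicity of Grade 3 or above, and that the stricter table reflects the intended rule for nonhematologic events. If Grade 2 was intended instead, the table is the text to correct; the conflict is the same.

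**What to change.** Either of two changes to the hold sentence in 7.2.2.1 removes the conflict.

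1. **Preferred.** Replace it with a reference to 7.2.2.3 for both the hold condition and the restart grade, by toxicity class and grade. This also closes the silence on controlled Grade 4 events. Section 7.2.2.3.2 already sends infusion-related reactions to 8.1.3.4.
2. **Alternative.** Keep the Grade 2 threshold for hematologic toxicity only, and state Grade 1 or lower, or baseline, for nonhematologic toxicity. This resolves the restart conflict, but a few words would still be needed to say that a Grade 4 event is held whether or not supportive care controls it.

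The cost is one sentence of protocol text. As an amendment it needs ethics review, and it can join another amendment at little extra cost. No design element, sample size or analysis changes.
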